At the centre of the logic model are the hypothesised pathways by which inputs are transformed into outcomes. The first of these is rooted in the circumstances of children and their parents and may include personal well-being (such as physical and mental health), relationships (with child and their partner), support networks, and neighbourhood quality (such as trust and safety). The second is

changes in project capacity denoted mainly by changes in how staff experience their job and their work; it may also include changes induced by the learning community. The third potential pathway is changes in service capacity such as improved local inter-agency cooperation or the implementation of national policy on early years such as the National Framework for Early Childhood Education (Síolta¹⁴) and Early Childhood Curriculum Framework (Aistear¹⁵).

Given the importance of pathways as active ingredients in how programmes work, it is worth documenting briefly some research evidence in support of the pathways which have been identified in the logic model. Beginning with the behaviour and attitude of parents and children, one study of Early Head Start in the US identified the parent-child relationship as a key pathway to improved outcomes for children¹⁶. Similarly, an evaluation of the Child-Parent-Centres in Chicago identified family and school supports for the child's education as key mediators of improved cognitive outcomes for the child, as well as reductions in child neglect and abuse¹⁷. The first phase of the evaluation of Sure Start in the UK found that, while there were relatively few impacts among children – fewer behaviour problems and greater social competence among the three year-old children of

14 Department of Education and Skills, 2010a.

15 National Council for Curriculum and Assessment, 2009.

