39 'The finding that empowerment is related to two of the eight measures of programme impact upon child and parenting outcomes, in particular two of the five parenting measures (9-month-old maternal acceptance, 36-month-old home learning environment), suggests that strengthening programme activities relevant to empowerment should improve their effectiveness in influencing parenting. Note that empowerment in this study is not a self report measure.' (Melhuish, Belsky, Anning, Ball, Barnes, Romaniuk, Leyland and the NESS Research Team, 2007:59).

40 'For despite much rhetoric about, and investment in, partnership working as the panacea for complex problems, we still know relatively little about the workings of these strategic partnerships and how they actually engage with, and improve, front-line practice and outcomes for service users. ... Indeed, we are in only the early stages of identifying evidence that such partnerships improve outcomes' (Morrison, 2010:313). A meta-analysis of the effectiveness of early years programmes found that 'comprehensive services are neither necessary nor sufficient for large sustained gains' (Barnett, 2011:977). In Ireland, a qualitative study of a five-year inter-agency process found that 'a good inter-agency process alone may not guarantee better outcomes' (McKeown, 2011; 2012).

agencies⁴¹, and also studies which show how the absence of inter-agency working contributes to system failures in protecting children from neglect, abuse or even death⁴². While this does not challenge the value of inter-agency working, or the link between service capacity and outcomes, it draws attention to the need for this evaluation to find out if inter-agency structures translate into changes in how front-line services are delivered and experienced by children and their parents.

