4.3 Does NEYAI have an impact?

We propose a quasi-experimental design⁴⁷ since, in the circumstances, this is the most appropriate way of answering the first evaluation question: does NEYAI have an impact on children and their parents by comparison with a matched sample of those who have not participated in NEYAI? This design involves comparing the treatment group (those who receive the 'NEYAI treatment') with a comparison group (those who receive the 'usual treatment'), both groups matched in terms of demographic and socio-economic characteristics. More specifically, this design involves three related elements:

- (i) assessing the treatment group at baseline (before the NEYAI intervention) and at follow-up (immediately after the NEYAI intervention) in order to measure any changes in the intervening period;
- (ii) assessing a matched comparison group at baseline (without any intervention other than 'treatment as usual') and at follow-up (using the same intervention period as the treatment group) in order to measure any changes in the intervening period;
- (iii) comparing changes in the treatment group and the comparison group in order to establish the difference in outcomes between NEYAI intervention and 'treatment as usual', thereby measuring the *net* impact of the intervention.

The measurement of difference in outcomes between the treatment and comparison groups - 'between-group differences' - is an acceptable and accepted way of measuring impact provided that all of the measured differences between the two groups are taken into account. However it also needs to be recognised that it is not a perfect comparison since, due to the absence of randomisation⁴⁸, there may be unmeasured differences between the two groups which could account for any difference in the observed net impact. The perfect comparison involves an experimental design, usually called a randomised control trial (RCT), but this is not an option since the NEYAI was not designed with that in mind and, moreover, could be difficult to design in practice. Nevertheless, the quasi-experimental method provides an important degree of confidence that,

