The instrument can also be completed by parents but their assessments tend to be give higher ratings for the child’s abilities. We are not in a position to evaluate the extent to which assessments by childcare staff might correspond with assessments by teachers. Despite this limitation, the assessments are being carried out by the same childcare staff at baseline and follow-up and this provides a consistent basis for comparing change in the intervening period.

In addition to the EDI, the Child Questionnaire includes a measure of the child's emotional regulation using the Emotion Regulation Checklist (ERC)⁸⁰. This is based on a growing body of evidence which suggests that a child's capacity for emotional self-regulation is a strong predictor of well-being generally⁸¹ as well as school-readiness and school outcomes⁸², and has been used in the assessment of pre-school children⁸³.

The Child Questionnaire also contains a measure of inter-agency working based on the rationale that, where this occurs, it will manifest at the front-line of service delivery for children and their parents. Three questions are used to measure inter-agency working: (i) has there been any contact with any other agency or service about the needs of this child during the previous four weeks; (ii) how many times there has been contact during the previous four weeks; and (iii) whether the response has been helpful. The questions, as worded, are suitable for the baseline (since some children may only be known to the childcare centre for 4 weeks) but will be adjusted to give a longer timeframe in the follow-up (since all children will be in the childcare centre for the previous school year). A similar set of questions are also asked in the Staff Questionnaire (Section D). Aspects of inter-agency working are also covered in the Parent Questionnaire (H2.6: 'Staff help me to contact other services when I need to') with a matched item in Staff Questionnaire (D3.6: 'I help parents to contact other services when they need to').

80 Shields and Cicchetti, 1997.

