9.2 Follow-up Data Analysis

The follow-up data analysis will involve the following components.

9.2.1 Repeat the analysis described in paragraphs 9.1.2, 9.1.3 and 9.1.4 above. This is necessary in order to make sure that, when baseline and follow-up data are merged, the latent variables underpinning the measurement and structural models are based on identical structure matrices and measurement scales. That is the only way of making valid comparisons between baseline and follow-up when using multi-dimensional outcome measures. This step will involve a recalibration of all latent concepts using the combined dataset since, only when these conditions are satisfied, will we be able to present robust ‘before-and-after’ comparisons of outcomes. The adjusted models of child, parent and staff outcomes will be presented graphically along with an interpretation of their meaning and implications.

9.2.2 Having established consistent and robust measurements for all multi-dimensional outcomes relating to children, parents and staff, we will present results on impact by comparing the difference between baseline and follow-up scores. Improvements in outcomes will be expressed in terms of a comparison of means, standard deviations and effect sizes. As explained earlier, the use of effect sizes is a simple way of standardising and comparing two sets of scores and allows the impact of NEYAI to be measured in a way that is comparable to other early years programmes. Table 3 is a draft of the format that will be used to present this data.

Table 3 Format for Presenting Effect Size Scores in the Final Report

Vari- able	Effect Size Score for Treatment Group (TG)												Effect Size Score for Comparison Group (CG)										
	BC	CC	CK	CN	DD	DL	FL	LD	LK	RO	TT	All	1	2	3	4	5	6	7	9	10	All	
*																							
**																							

*Denotes a statistically significant difference between treatment group and comparison group for that variable.

**Denotes a statistically significant difference between treatment group or comparison group and the GUI for that variable.

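### Inter-agency contact is asked over four weeks at baseline and over an unstated longer window at follow-up, so raw change is confounded with window length and net change is biased if baseline rates differ

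*Protocol*

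**What the plan says.** Section 6.1 (Child Questionnaire) measures inter-agency working with three questions, listed as H3.1-3.3 in Appendix Three. The first is "has there been any contact with any other agency or service about the needs of this child during the previous four weeks", the second is "how many times there has been contact during the previous four weeks", and the third asks whether the response was helpful. The section explains that this wording suits baseline because a centre may have known some children for only four weeks. At follow-up the questions "will be adjusted to give a longer timeframe in the follow-up", "since all children will be in the childcare centre for the previous school year". The follow-up length is not given, and nothing is said about rescaling or about asking the four-week questions again.

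Three other places bear on this:

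- Section 3 makes service capacity the third hypothesised pathway, described as "changes in service capacity such as improved local inter-agency cooperation". It also draws attention to "the need for this evaluation to find out if inter-agency structures translate into changes" in front-line delivery.
- Section 4.3 defines impact by "comparing changes in the treatment group and the comparison group in order to establish the difference in outcomes between NEYAI intervention" and usual care. The comparison group is assessed over the same period.
- Section 9.2.1 requires, before baseline and follow-up data are merged, that "latent variables underpinning the measurement and structural models are based on identical structure matrices and measurement scales".

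**The concern.** Other things equal, a longer recall window catches more contacts and makes at least one contact more likely. When the window changes between waves, a rise can appear although nothing at the centre has changed. The stated reason explains why baseline must be short. It does not explain why four weeks could not be asked again at follow-up.

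The comparison group does not fully protect against this. A longer window multiplies each group's count, so it also multiplies any gap between the groups that was there at baseline. Section 4.3 accepts that the groups may differ in unmeasured ways, and section 5.2 matches areas on deprivation scores and not on family characteristics. A pre-existing difference in contact could then be read as the programme strengthening (or weakening) inter-agency work, and could enter the pathway models in that form.

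Timing matters too. This is questionnaire wording: an analysis plan can choose how to model an item, but it cannot supply a four-week answer that was never collected.

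**Working it through.** The protocol gives no figure to reproduce here. The check is an illustration on assumed inputs.

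**Inputs**

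- Baseline window: 4 weeks (section 6.1).
- Follow-up window W: longer than 4 weeks, length not stated. Assumed 12, 26 and 40 weeks.
- Contact rate L per child per four weeks: not stated. Assumed 0.1 to 0.3.
- Impact measure: treatment-group change minus comparison-group change (section 4.3).

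**Formulas**

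- Expected count over W weeks = L × W/4.
- Probability of any contact = 1 − exp(−L × W/4), taking contacts as Poisson with one rate for all children.

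The count formula needs only a constant mean rate. The any-contact formula is more fragile: if contacts cluster in a few children with special needs, it rises less than shown.

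**Step 1. One group, L = 0.2, no real change**

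| Window | Mean count | Any contact |
|---|---|---|
| 4 weeks (baseline) | 0.20 | 18.1% |
| 12 weeks | 0.60 | 45.1% |
| 26 weeks | 1.30 | 72.7% |
| 40 weeks | 2.00 | 86.5% |

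The whole rise comes from the window.

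**Step 2. Net change, no real change in either group**

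For counts, net change = (W/4 − 1) × (treatment rate − comparison rate). At 26 weeks with rates 0.2 and 0.1: (1.30 − 0.20) − (0.65 − 0.10) = 1.10 − 0.55 = 0.55.

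| Rates, treatment v comparison | 12 weeks | 26 weeks | 40 weeks |
|---|---|---|---|
| 0.2 v 0.2, count | 0.00 | 0.00 | 0.00 |
| 0.2 v 0.1, count | 0.20 | 0.55 | 0.90 |
| 0.2 v 0.1, any contact (percentage points) | 10.6 | 16.3 | 14.6 |
| 0.3 v 0.2, count | 0.20 | 0.55 | 0.90 |
| 0.3 v 0.2, any contact (percentage points) | 6.4 | 5.2 | 0.8 |

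Equal rates give exact cancellation. Unequal rates give a false net change with the sign of the baseline gap: swapping 0.2 and 0.1 gives −0.20 to −0.90 for counts.

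**Step 3. A real effect: treatment rate rises from 0.1 to 0.2, comparison stays at 0.1**

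The net change in counts is 0.30, 0.65 and 1.00 at 12, 26 and 40 weeks, against 0.10 with four weeks at both waves. A real effect still shows, on a stretched scale.

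**Step 4. Two remedies tested**

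- Four weeks at both waves, constant rates: expected change is 0 in each group and between groups, for both items, whatever the baseline gap.
- Follow-up counts rescaled to four weeks (26 weeks, 0.2 v 0.1): 1.30/6.5 = 0.20 and 0.65/6.5 = 0.10, so both changes are 0. This needs a known window and equally complete recall over both windows. The yes/no item cannot be rescaled without a model.

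**The case against.** The case against is substantial, and much of it stands.

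- A reader might infer that any observed change in inter-agency contact is an artefact, or that no change can be computed. The protocol does not support that. A real change can lie within the observed one (step 3), the artefact cancels between groups when baseline rates are equal, and a follow-up-only comparison uses a single window.
- Counts can be analysed as rates, and the protocol nowhere commits to subtracting unscaled counts. Questions G1 and G2-4 in Appendix Three record how long staff have worked with the child and how long the child has attended, which could help set exposure time. Such modelling normally belongs in an analysis plan. But a rate needs a stated window and comparable recall over four weeks and over many months, and section 6.1 secures neither.
- A reader might infer that section 9.2.1 is breached outright. Its identical-scales condition is stated for latent variables and multi-dimensional outcome measures. These are short bespoke items, so it applies only by extension.
- The measure is not the sole source on this theme. Parent item H2.6 and staff item D3.6 are quoted without a recall window, and section 9.2.4 assigns linkages between services largely to case-study data. H2.6 and D3.6, however, ask whether staff help parents reach other services, not whether an agency was contacted about a given child.
- Contact over the intervention year may be the more relevant exposure for a pathway model. That supports asking it as well, with its own stated window. It does not support dropping the four-week item.
- The helpfulness question has no mechanical link to window length and is not part of this point.

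**Conclusion.** The point holds in a limited form. With an unstated longer window at follow-up, raw change in any contact and in number of contacts cannot be separated from window length. The between-group difference in change is unbiased on this account only if the groups start with equal contact rates, which a non-randomised design cannot guarantee. The size of the bias is unknown. The range of 0.20 to 0.90 contacts per child rests on assumed rates of 0.2 and 0.1 per four weeks, assumed windows of 12 to 40 weeks, constant rates over time and plain subtraction of counts.

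This is a cheap improvement to a pathway measure. It does not undermine the evaluation: the text does not name these items among the child, parent or staff outcomes. It should be settled before follow-up, because the comparable item cannot be recovered later.

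**What to change.** In section 6.1, and in the follow-up Child Questionnaire, keep the any-contact and number-of-contacts questions with identical four-week wording in both groups. State that change from baseline uses these items only.

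If contact over the school year is wanted, for example as exposure in the pathway models, add it as a separate follow-up question with a stated window. Compare it between groups at follow-up or analyse it as a rate. Do not treat it as change from the four-week baseline. There is no need to confine it to descriptive use.

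The cost is a few extra items in the follow-up questionnaire. Sampling, baseline collection and timetable are unchanged.

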6.2 Parent Questionnaire

The purpose of the Parent Questionnaire is to assess the well-being of each mother across a wide range of domains that are recognised as central to personal well-being and the well-being of children. The Parent Questionnaire will be completed using a face-to-face interview with the mother of the 'focus child', the latter defined as the child attending the childcare centre who has been randomly selected to participate in the evaluation. Each parent will be interviewed in the home, or elsewhere if that is her preference, and at a time that is agreed with the interviewer⁸⁴. The Parent Questionnaire is similar to a questionnaire that has been used in numerous studies by members of the research team⁸⁵ – with the addition of some new instruments, some of them from the GUI – and for that reason, it is considered unnecessary to pilot it.

[figure not shown]
The conceptual framework underpinning the Parent Questionnaire is graphically illustrated in Figure 4. There is a detailed guide to every question in Appendix Four and the actual questionnaire is in a separate document. The conceptual framework informing the Parent Questionnaire has already tested in previous work (see Figure 2 above) and this is being further re-analysed using the GUI⁸⁶ dataset. This framework envisages parental well-being as a latent construct which manifests through the parent's personal and relationship experiences and is itself influenced by the parent's personality traits, socio-economic and neighbourhood characteristics, etc.

84 The decision to interview mothers only is based entirely on practical considerations since interviewing fathers as well as mothers is beyond the resources of the evaluation. However the Parent Questionnaire contains two questions on the father's involvement with the child, based on similar questions used in the GUI, the Sure Start evaluation and the Millennium Cohort Study: 'How often can you count on him if you need him to take care of the child?' and 'Overall how close would you say he is to your child?'

85 McKeown, Haase, Pratschke, Lanigan, Burke, Murphy, and Allen, 2008:23-28; McKeown and Haase, 2007; Haase, McKeown, and Pratschke, 2008; Haase, 2009.

86 Pratschke, Haase and McKeown, 2011. GUI refers to Growing Up in Ireland: National Longitudinal Study of Children; available at: www.growingup.ie. GUI is based on two cohorts of children: 8,570 nine-year old children on whom data was collected 'between September 2007 and June 2008' (Williams, Greene, Doyle, Harris, Layte, McCoy, McCrory, Murray, Nixon, O'Dowd, O'Moore, Quail, Smyth, Swords and Thornton, 2009:16); and 11,100 nine-month old children on whom data was collected 'between September 2008 and April 2009' (Williams, Greene, McNally, Murray and Quail, 2010:21).

Figure 4 Conceptual Framework Informing Parent Questionnaire

In addition to this theoretical understanding, the selection of instruments is also informed by whether they have been used previously in similar evaluations and studies. Specifically, we have adopted instruments that have been used in the GUI since this will facilitate comparison of the initiative with nationally representative benchmarks. Of note is the fact that some of the longer multi-item questions from the GUI have been shortened, notably F1-2 (Pianta Child-Parent Relationship Scale), F8 (Parental Stress Scale), and G1-G7 (Dyadic Adjustment Scale); this was done following

latent variable analysis⁸⁷ and resulted in deleting those items which added little to the overall measurement of the concept or its components.

6.3 Staff Questionnaire

The purpose of the Staff Questionnaire is to assess the capacity of staff. It is widely recognised that staff capacity is a key ingredient in childcare services, as outlined above, and this is also a core assumption underpinning the NEYAI. At the same time, the measurement of staff capacity is far from straightforward and, within the constraints of self-report instruments, it is difficult to find instruments that are specifically tailored to the requirements of staff in the early years sector. Within these constraints therefore we have devised a bespoke instrument, albeit with measures widely used in other contexts. The Staff Questionnaire will be completed on-line by all childcare staff in each centre participating in the evaluation, excluding administrative and support staff. The questionnaire has been piloted in two childcare centres – which are not part of this evaluation - and can be completed in about 30 minutes.

The conceptual framework underpinning the Staff Questionnaire is graphically illustrated in Figure 5. There is a detailed guide to every question in Appendix Five and the actual questionnaire is in a separate document.

The conceptual framework informing the questionnaire is based on an understanding of work, and therefore staff capacity, as having an ‘outer’ and an ‘inner’ aspect. The outer aspect is conventionally referred to as the ‘job’ which we measure, using standardised instruments, through qualifications and the job experience of staff in terms satisfaction, commitment, pressure, autonomy, consultation, staff-management relations, support and engagement. By contrast, the inner aspect is the relationship which staff perceive themselves to have with the ‘object’ or ‘essence’ of their work which, in this case, is the children and their parents. This inner aspect is foundational to all work but is particularly important in work that is generative of human development such as the teacher-pupil relationship, the master-apprentice relationship or, more generally, the adult-child relationship⁸⁸.

87 Latent variable analysis involves using factor analysis to identify the underlying or ‘latent’ variable which is shared, conceptually and statistically, by a set of measured items. In other words, measured items which are highly inter-correlated are assumed to form a common unmeasured latent variable which manifests through those items.

88 The psychologist Carl Jung has written about this relationship: ‘An understanding ear is everything in a teacher, and cannot be esteemed highly enough. One looks back with appreciation to the brilliant teachers, but with gratitude to those who touched our human feelings. The curriculum is so much necessary raw material, but warmth is the vital element for the growing plant and for the soul of the child (Jung, 1953). The memoirs of Irish writer and Principal of a primary school in Kerry, Bryan McMahon, capture a similar understanding of teaching: ‘each child had a gift, and that the ‘leading out’ of that gift was the proper goal of teaching. To me a great teacher was simply a great person teaching. ... he should never cease to promote in children the determination to say “yes” to life, to the dark as well as to the bright of it, to its beauty and glory, to its lapses from grace into degradation and its eventual restoration to serenity’ (McMahon, 1992:8 and 83). The psychoanalyst Eric Fromm has also written about this relationship but from the perspective of the adult:

Central to this relationship is the capacity of the teacher / master / adult to see and nurture the unique potential of the person in their care, and to cultivate what Jung calls ‘the soul of the child’⁸⁹. In the context of childhood education, it has been described as the capacity to ‘open the windows of wonder’ for the child by the noted teacher and writer, Bryan McMahon⁹⁰. Specialists in early childhood education increasingly refer to this as the capacity for ‘sustained shared thinking’⁹¹ or ‘extended purposive conversations’⁹². These insights are reflected in the importance given to ‘interactions’ in both the National Framework for Early Childhood Education (Síolta⁹³) and the Early Childhood Curriculum Framework (Aistear⁹⁴). This capacity, often acknowledged in (auto)biographical accounts of how talent is nurtured through the encouragement and engagement of an interested adult, is central to our understanding of capacity in the childcare setting.

‘The teacher is taught by his students, the actor is stimulated by his audience, the psychoanalyst is cured by his patient – provided they do not treat each other as objects, but are related to each other genuinely and productively’ (1956:24).

89 Jung, 1953.

90 He wrote of teaching as ‘opening the windows of wonder’ (McMahon, 1955) and observed that his school was ‘fortunate that the infant teachers encouraged the emergence of a personality among the infants. ... We were far-sighted enough to appreciate that encouragement at the chrysalis stage would serve him all his life’ (McMahon, 1992:80).

[figure not shown]
91 Sustained shared thinking is defined as ‘any episode in which two or more individuals ‘worked together’ in an intellectual way to solve a problem, clarify a concept, evaluate activities, extend a narrative, etc. To count as sustained shared thinking, both parties had to be contributing to the thinking and it had to be shown to develop and extend thinking’ (Siraj-Blatchford, 2010a:157).

92 Extended purposive conversations are conceptually the same as sustained shared thinking but French has suggested that ‘extended purposive conversations’ may be a more appropriate term because ‘it puts the focus on extending the conversation ‘by listening to and engaging children with conscious purpose and intent, encouraging them to articulate their discoveries and their learning. The emphasis on ‘conversation’ is perhaps more concrete, grounded in practice, and easier than ‘thinking’ for educators to conceptualise as a goal for working with young children’ (French, 2011:74).

93 Standard 5 (of 16) states: ‘Fostering constructive interactions (child/child, child/adult and adult/adult) requires explicit policies, procedures and practice that emphasise the value of process and are based on mutual respect, equal partnership and sensitivity.’ (Department of Education and Skills, 2010a:39).

94 One of the four guidelines for good practice is ‘learning and developing through interactions’. It states: ‘Relationships are at the very heart of early learning and development. Through their early interactions babies learn to feel secure, to communicate, and to enjoy being with people. As they grow and develop, toddlers and young children love to play, to chat, to watch, and to be with others. Children build relationships, communicate, express love and affection, play together, learn, and have their needs met through contact with others. These guidelines identify a range of interaction strategies and methods which the adult can use to enhance children’s learning and development.’ (National Council for Curriculum and Assessment, 2009:27).

Figure 5 Conceptual Framework Informing Staff Questionnaire

We measure this inner aspect of capacity using three bespoke self-report measures of how staff relate to children and their parents. The first of these focuses on staff sensitivity to the child, staff capacity to stimulate the child, and respect for the child’s autonomy; these dimensions are derived from the Adult Engagement Observation Schedule⁹⁵. The second measure focuses on how staff interact with children in order to promote each child’s thinking and language, drawing on Síolta, Aistear and the work of French⁹⁶. The third measure focuses on how staff interact with parents in

95 Bertram, 1996:Ch 4; Pascal and Bertram, 1999.

96 French, 2011.

order in order to promote each child's learning and development, again drawing on Síolta and Aistear.

On the right-hand-side of Figure 5 we list the possible determinants of staff capacity. These are mainly the same as the measures of well-being used in the Parent Questionnaire, based on the assumption that, since child development is influenced by these aspects of parental well-being it is likely to be similarly influenced by the same aspects of staff well-being⁹⁷.

We expect the Staff Questionnaire to provide useful insights into the capacity of childcare staff. However an important limitation is that we have no independent observation or assessment of staff interactions with children. This is a significant limitation since staff self-reports may not correlate with staff behaviour. We are not in a position to overcome this limitation since direct observation of staff is outside the resources available for the evaluation. At the same time, this limitation also applies to the Parent Questionnaire and it is well-known that parental self-reports are highly predictive of outcomes for their children.

